The study will be conducted in public health facilities of Sidama national regional state. It is located about 275 Kilometers away from Addis Ababa. It has 30 Districts, 1 city administration and 6 town administration with a total of 576 kebeles of which 524 of them are rural and 52 are urban. It is one of the highly populated areas in Ethiopia, having a total population of about 4 million people residing on 72100 hectare of land. Out of the total population 5.7% are urban and 94.3% rural residents. Sidama is characterized by three agro-ecological zones: the dry midlands/lowlands (20%), the midlands (48%) and the highlands (32%). In Sidama region mixed agriculture (crop and livestock production) is practiced. Major crops grown include: enset, coffee, maize, wheat, teff, barley, haricot bean and khat. Enset is the main staple crop both in highlands and midlands while maize is so in the lowlands. There are two cropping seasons in Sidama Zone: belg and meher. Belg rains are mainly used for land preparation and planting of long cycle crops such as maize and sorghum and seed bed preparation for meher crops. The meher rains are used for planting of cereal crops like barley, teff, wheat and vegetable crops. Besides, meher rains are also responsible for the growth and development of perennial crops such as enset,

coffee and khat. Food security is more precarious in the lowland areas of Aleta Wondo, Borecha, Darra, Bensa, Loka Abaya and Hawassa Zuria woredas mainly due to moisture stress and water logging in some pocket areas hampering agricultural production, less diversification of food sources and minimum use of improved farm inputs due to lack of cash and credit facilities to purchase the inputs. The Sidama region administration has a total of 4063 health professional of different disciplines and 524 Health Posts, 127 Health Centers, 1 general and 12 District hospital owned by government and additionally there are 21 private and 3 NGO clinics, 65 private rural drug venders. The overall potential health service coverage of the Zone by public health facilities are 90.3%.

Study design

a prospective cohort study design will be conducted from March 1 2022 to November 30 2022

Source population

All pregnant women attending ANC clinic at public hospitals of Sidama region.

Study population

Pregnant women selected by using simple random sampling technique from the prior three months ANC register of selected public hospitals and meet inclusion criteria

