Eligibility criteria

Inclusion Criteria

Attend ANC in the last 3 months

Permanent residence with possible contact

Plan to deliver in the region

Exclusion Criteria

Severe anemia / sever illness

Sample size determination

Sample size calculation for the second objective

The sample size for Exposed and Non-Exposed is calculated using Epi Info version 7 soft-ware by taking a proportion of low birth weight among non anemic women of 14.6%, AOR of 3.17, study power of 80%, an Exposed to Non-Exposed ratio of 1:1 and a non-response rate of 15%. Finally a total of 180 (90 Anemic mothers and 90 non-anemic mothers) sample size was calculated.

Table 1: Sample size calculation

| Factors | Ratio of controls to cases | % of outcome in unexposed | AOR | Power | CI | Exposed | Non Exposed | Final sample size | Source |
|---------|----------------------------|---------------------------|------|-------|-----|---------|-------------|-------------------|---------|
| Anemia | 1:1 | 14.6 | 3.17 | 80 | 95% | 78 | 78 | 156 | AZ |
| Anemia | 1:1 | 11.2 | 3.81 | 80 | 95% | 68 | 68 | 136 | Sodo |
| Anemia | 1:1 | 13.02 | 3.51 | 80 | 95% | 70 | 70 | 140 | Kembata |

Sampling techniques

From 18 public hospitals found in the region we randomly selected 6 hospitals. Enumeration of prior three month's ANC register was conducted. Then, based on the number of ANC register, the sample size was proportionally allocated for all selected public hospitals in the region (Figure 1).

Exposed (pregnant women having anemia) and non-exposed (pregnant women not having anemia) will be selected by using simple random sampling technique from the prior three months ANC register of each selected public hospital and followed until delivery to see the incidence of low birth weight.

[figure not shown]

Figure 2: Schematic representation of sampling procedure

Study variables

Dependent variable: Birth Weight

Independent variable

- Socio-demographic factors
- Reproductive related
- Medical related
- Health promotion
- Anemia

Operational definitions

Anemia: any hemoglobin level below 11g/dl in pregnancy is considered as anemia (5,6).

Weight (Kg): will be measured by electronic scales with digital display (UNICEF SECA Electronic weight scale (± 10 precision scale) and Participants will be asked to remove their shoes and any bulky clothing during measurement will be taken.

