Three day intensive training will be given on how to perform standardized height and weight measurement and on interviewing techniques using standard checklist and structured questionnaire. The checklist and questionnaires will be translated into a regional working language (Sidamu Affo). Supervision will be conducted. Double data entry will be done and the questionnaire will be pretested on 5 % of total sample size at Dilla city. The calibrated instrument will be used to measure height and weight.. During data collection, continuous supervision will be done by the supervisors and principal investigator.

Data processing and analysis

The data will be entered into Epidata software and exported to SPSS software for windows version 23. for analysis. Descriptive statistics will be computed and both bivariable and multivariable logistic regression will be employed to identify effect of anemia on birth weight Independent sample student t test will be used to compare the mean difference in birth weight in anemic and non-anemic pregnant women. Multi variable Logistic Regression will be done to establish association of anemia with birth weight.

Ethical consideration

Prior to data collection appropriate ethical clearance and supportive letter will be obtained from the Ethical Review Committee of Hawassa College of Health Science. Written permission will be obtained to undertake the study from the selected hospitals. Participation in the study will be based on voluntary base and the participants

will be informed about the right to withdraw at any time from the study. Confidentiality will be assured by using anonymity. Pregnant women who had anemia (Hb<11g/dl) will be provided with Iron-folate tablets. Written consent will be requested from every study participant included in the study during data collection time after explaining the objectives of the study. For this purpose, a one page consent letter was attached to the cover page of each questionnaire stating about the general objective of the study and issues of confidentiality which was discussed by the data collectors before proceeding with the interview.

Work plan

Table 2 : Showing the work plan of the study in Sidama Region, 2022

| Activity | Oc t | Nov | De c | Jua n | Fe b | Mar | Ap r | May | Ju n | Jul | Au g | Se p | Oc t | No v | De c |

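### Women are selected hospital by hospital, but hospital is in no variable list, printed form or stated analysis, so the pooled estimate is open to site confounding if the anemic share differs between hospitals

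*Protocol*

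**What the plan says.** Under Sampling techniques, the protocol states "From 18 public hospitals found in the region we randomly selected 6 hospitals" and then "based on the number of ANC register, the sample size was proportionally allocated for all selected public hospitals in the region". Exposed and non-exposed women are to be "selected by using simple random sampling technique from the prior three months ANC register of each selected public hospital". The 1:1 ratio appears only for the whole study, as 90 anemic and 90 non-anemic women (Sample size determination). The text does not say whether it holds inside each hospital.

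Study variables lists five groups: socio-demographic, reproductive, medical, health promotion and anemia. Hospital is not among them. The printed questionnaire has no hospital item; its only geographic item is rural or urban residence.

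Data processing and analysis names descriptive statistics, an independent-samples t test on birth weight, bivariable logistic regression and a multivariable model: "Multi variable Logistic Regression will be done to establish association of anemia with birth weight". No stratification, site term or other allowance for hospital is mentioned.

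Study area describes lowland, midland and highland zones and says "Food security is more precarious in the lowland areas", naming the districts. Statement of problem says that the contribution of the different causes of anemia depends heavily on location.

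**The concern.** Hospital is part of the design: it fixes how many women come from where and which register they are drawn from. A factor used to build the sample should normally appear in the analysis, the more so when the protocol itself gives reasons to expect sites to differ in anemia and in nutrition.

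What is at stake depends on the split within hospitals. If hospitals with more anemic women in the sample also have a higher risk of low birth weight for other reasons, the pooled comparison credits anemia with part of the site difference. The opposite pattern would hide part of a real effect. The protocol wants to close a gap in inferring causality between anemia and low birth weight, so this kind of bias goes to its purpose. If the split is 1:1 everywhere, hospital cannot confound at selection, and the loss is one of efficiency.

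**Working it through.** **1. The plan's own figure.** Inputs from Sample size determination: "taking a proportion of low birth weight among non anemic women of 14.6%, AOR of 3.17, study power of 80" percent, two-sided 5% level (95% confidence in Table 1), 1:1, 15% non-response.

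- Risk in anemic women: p1 = 3.17 × 0.146 / (1 − 0.146 + 3.17 × 0.146) = 0.3515.
- The two-proportion formula gives 69 per group without continuity correction and 78 with it. Table 1 states 78, so it reproduces.
- Total: 156 × 1.15 = 179.4, rounded up to 180, as stated.

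This formula treats the women as independent individuals and contains no hospital component.

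**2. Expected outcome events.** 78 × 0.146 + 78 × 0.3515 = 11.4 + 27.4 = 38.8, about 39 low-birth-weight births among 156 evaluable women.

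**3. Unequal anemic share, no true effect.** The documents give no hospital-specific figures, so these are assumptions. Take two equal groups of hospitals, with anemia having no effect inside either.

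| Assumed LBW risk | Assumed anemic share of sample | Pooled risk, anemic | Pooled risk, non-anemic | Pooled OR |
|---|---|---|---|---|
| 25% / 12% | 60% / 40% | 0.6×0.25 + 0.4×0.12 = 0.198 | 0.4×0.25 + 0.6×0.12 = 0.172 | 1.19 |
| 25% / 10% | 65% / 35% | 0.65×0.25 + 0.35×0.10 = 0.1975 | 0.35×0.25 + 0.65×0.10 = 0.1525 | 1.37 |

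First row: (0.198/0.802) / (0.172/0.828) = 1.19. Second row: (0.1975/0.8025) / (0.1525/0.8475) = 1.37. Stratified by hospital group, both are 1.00.

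A wider set of assumptions (anemic share from 20%/30% to 10%/50%, LBW risk from 12%/17% to 8%/24%) gives null pooled odds ratios from 1.06 to 1.71. With a within-hospital odds ratio of 3.17, the same range gives pooled values of 3.32 to 5.21.

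**4. 1:1 in every hospital.** With no true effect the pooled odds ratio is 1.00 whatever the site risks. With a within-hospital odds ratio of 3.17 it is slightly attenuated, because the odds ratio is not collapsible:

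- Site risks 12%/17% in non-anemic women: the anemic risks are 0.302 and 0.394, mean 0.348, against 0.145. OR = 3.14.
- Site risks 8%/24%: the anemic risks are 0.216 and 0.500, mean 0.358, against 0.160. OR = 2.93.

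In this case the t test also leaves between-hospital variation in birth weight in its error term, so its standard error is larger than the design requires. The documents give no between-hospital variance, so this cannot be sized.

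**5. Scale against sampling error.** With 90 per group and the first-row risks, SE(log OR) = √(1/17.82 + 1/72.18 + 1/15.48 + 1/74.52) = 0.38. The bias is ln 1.19 = 0.17, about 0.45 SE. For the second row, ln 1.37 = 0.31 is about 0.8 SE.

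**The case against.** Several points on the other side have force.

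- **The split may already be 1:1.** The sampling schematic (Figure 2) is not visible in the text reviewed and may show exposed and non-exposed numbers per hospital. If it shows 1:1 throughout, the confounding argument falls away at selection. This stands, and the fix allows for it. Uneven loss within the 15% non-response allowance could still disturb the balance.
- **The form is not the whole data record.** The printed questionnaire has no participant identifier and no item for birth weight, the outcome. The absence of hospital is therefore weak evidence that it will not be known. This also stands; but nothing says it will be recorded, and a later analysis plan cannot adjust for a site that was not kept.
- **The multivariable covariates are open.** A reader might infer that every analysis ignores hospital. The document supports this only for the t test and the bivariable regression. The multivariable model lists no covariates, and an analysis plan not seen here could add hospital.
- **The size is hypothetical.** The site figures are assumed, the odds ratios are crude although a multivariable model is planned, and the bias is below one standard error.

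Three further readings are tempting but unsupported. Malaria is not left uncontrolled: it is recorded for each woman and is available as a covariate. Food security itself is not recorded, but income, extra meals and MUAC are partial proxies. Nor do the documents show that the anemia cut-off needs correction for altitude. They apply "any hemoglobin level below 11g/dl in pregnancy is considered as anemia" consistently, and give neither the altitudes nor the locations of the selected hospitals; a cited title about haemoglobin adjustments is not enough. Finally, the omission does not invalidate the sample size. A design effect of 1 + (30 − 1) × ICC would not apply directly, because anemic and non-anemic women are compared within the same hospitals.

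**Conclusion.** The concern holds in a conditional form and should be acted on. Hospital structures the sample and is missing from the variable groups, the printed form and the stated analyses; two of the named analyses cannot take it into account.

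If the anemic share of the sample varies between hospitals along with the risk of low birth weight, the pooled odds ratio is biased. Under the main illustrative assumptions it is about 1.2 to 1.4 when the truth is 1. If selection is 1:1 in every hospital, the cost is slight attenuation (3.17 becomes 2.93 to 3.14 in the cases worked) and an unquantified loss of precision in the t test. The document does not settle which case applies. Hospital-specific anemia shares and LBW risks are assumptions throughout. The calculation behind 180 women reproduces and is not in question.

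**What to change.** 1. Record the hospital for each woman on the data form.
2. State that anemic and non-anemic women are selected 1:1 within each hospital's allocation, or confirm this if the sampling figure already shows it. Where a register cannot supply equal numbers, report the achieved split by hospital; the stratified analysis still removes the between-hospital difference.
3. Fit hospital as a fixed stratum in the logistic model, either by conditional logistic regression or with five hospital indicators. Cluster-robust standard errors are not a good substitute with only six hospitals.
4. Replace the independent-samples t test with a linear model for birth weight on anemia, adjusted for hospital.

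The cost is one form field, a sentence on selection and a few sentences of analysis text. Five indicators use 5 degrees of freedom against about 39 expected events. Conditional logistic regression estimates no hospital parameters, so it is the more economical choice once other covariates enter. No change to the sample size is needed.

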Low birth weight is not only a predictor of prenatal morbidity and mortality, but studies have found that it also increases the risk for non-communicable diseases such as diabetes mellitus and cardiovascular diseases in later life (10-11)

The global magnitude of LBW is 15.5 %. In Ethiopia, the prevalence of under-five mortality ranges from 53 to 169 per 1000 live births out of this neonatal mortality which is mainly attributed by LBW accounts the largest portion (12)

In multiple studies, different factors have been identified as determinant for LBW, and among these are young maternal age at pregnancy, birth order, the family's income, maternal under nutrition, maternal underweight, pregnancy related complications, preterm birth, chronic medical illness, multiple pregnancies, history of previous LBW, insufficient prenatal care, and maternal smoking (13 14 15 16).

Statement of problem

Consequences of anemia include increased maternal and perinatal mortality, impaired physical and cognitive development of children and reduced work productivity (9)

Severe anemia (<7 g/L) during pregnancy has been associated with major maternal and fetal complications. It increases the risk of preterm delivery, low birth weight, intrauterine fetal death, neonatal death, maternal mortality, and consequently infant mortality. (17)

Pregnant woman that live in rural areas [18], lack of raw vegetables in their diet [19], illnesses [18] and low levels of education [20] are also major determinants of anemia. Similarly, anemia prevalence decreases as wealth status increases [21.],

Further, studies conducted in Ethiopia have shown that the type of residence, gravidity, interval between pregnancies, and malaria infection during pregnancy have been associate with gestational anemia. (22)

Working to improve the nutritional status of pregnant women through supplementation of vitamin A, iron, and iodine is important to minimize the risk of anemia [23]

The reason of anemia during pregnancy in developing countries includes nutritional deficiencies of iron, folate, and vitamin B12 and parasitic diseases, such as malaria and hookworm. The relative contribution of each of these factors to anemia varies greatly by geographical location, season, and dietary practices [1].

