Height (m): will be measured using a portable stadiometer with a sliding head plate, a base plate and connecting rods marked with a measuring scale. Participants will be asked to remove their shoes.

Birthweight: birthweight of newborn is the first weight of the newborn obtained after birth. Newborn birth weight is normal if it is $\geq 2,500$ g. And lower birth weight if it is $< 2,500$ g irrespective of the gestational age (42)

Intestinal parasite: presence of ova/parasite of hookworm, *Tenia* species, *Ascaris lumbricoides* and *S.stercoralis*

IPV: A behavior within an intimate relationship that is bound to result in physical, sexual, or psychological harm to the other partner or spouse (43).

Data collection procedure

A Data will be collected using a structured questionnaire and anthropometry measurements

A total of 12 Midwives and 6 supervisors will be involved in the data collection process.

The questionnaire included information on socio-demographic factors and obstetrics characteristics.

Anthropometric assessment

Height measurement will be performed with the aid of a measuring tape. The respondents will be asked to remove footwear, hair accessories that may obstruct measurement. A ruler will be placed on top of their heads, and the reading will be taken from the top of the ruler at eye level. Height will be then read and recorded to the nearest 0.1 cm. A calibrated bathroom scale will be used to measure weight. The device will be placed on a level surface. Each respondent will be asked to stand at the centre of the scale, barefoot with minimal clothing and empty pockets. The weight will be recorded to the nearest 0.1 kg.

To reduce intra individual error, height and weight will be measured twice and the mean value will be used for analysis. Anthropometric indices will be calculated using WHO Anthro software version 3.2.2.

Measurement of Birth weight

Data for birth weight will be recorded using the metric scale (in grams). During data collection, birth weight will be confirmed by weighing the baby using the metric scale (in grams). Documented evidence on the child health card or verbally from the mother will only be used if the baby is ill.

Data quality control

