|---------------------------------------|---------|-----|---------|----------|---------|-----|---------|-----|---------|-----|---------|---------|---------|---------|---------|
| Research proposal Preparation | | | | | | | | | | | | | | | |
| Final proposal submission and Defense | | | | | | | | | | | | | | | |
| Obtaining ethical Clearance | | | | | | | | | | | | | | | |
| Giving training | | | | | | | | | | | | | | | |
| Data collection and processing | | | | | | | | | | | | | | | |
| Final paper Submission | | | | | | | | | | | | | | | |
| Defense and dissemination of result | | | | | | | | | | | | | | | |

Questionnaire on birth weight

Socio-demographic characteristics of pregnant women public health facilities (N=180).

| Variables | Coding categories | Skip |
|--|---|-------------|
| Age | _____ | |
| Residence | 1. Rural 2. Urban | |
| Marital status | 1. Never married 2. Married 3. Separated/Widowed | |
| Religion | 1. Orthodox 2. Catholic 3. Protestant 4. Muslim 5. (Specify) | |
| Highest Educational level | | |
| Highest Husband Educational level | _____ | |
| Occupation status | 1. Government employee 2. Private employee 3. Merchant 4. House wife 5. (Specify) | |
| Family income | _____ | |
| Family size | _____ | |
| Sex of the newborn | 1. Female 2. Male | |
| Obstetric and baby characteristics of mothers who gave birth at the selected public Hospitals | | |
| Current pregnancy type | 1. Planned 2. Unplanned | |
| Gravidity | | |
| Fertility desire | | |
| Injury history of any source | 1. Yes 2. No | |
| Trimester at 1st visit for the last pregnancy | 1. 1 st 2. 2 nd 3. 3 rd | |
| TT vaccine before or during pregnancy | 1. Yes 2. No | |

| | | |
|---|---|--|
| Iron supplementation for current pregnancy | 1. Yes 2. No | |
| Dietary counseling during the current pregnancy | 1. Yes 2. No | |
| Extra meal during current pregnancy | 1. Yes 2. No | |
| History of abortion | 1. Yes 2. No | |
| History of still birth | 1. Yes 2. No | |
| Obstetric and baby characteristics of mother who gave birth at the selected public Hospitals | | |
| APH during the current pregnancy | 1. Yes 2. No | |
| Substance use during the current pregnancy | 1. Yes 2. No | |
| Alcohol use during the current pregnancy | 1. Yes 2. No | |
| Chronic medical illness | 1. Yes 2. No | |
| Reproductive characteristics of respondents | | |
| Used modern contraceptive | 1. Yes 2. No | |
| Time to book first ANC visit | 1. ≤ 16 weeks 2. > 16 weeks | |

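### Birth weight is defined as the first weight after birth, but the measurement rule uses an untimed study weighing and allows the card or the mother's word only for ill babies

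*Protocol*

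**What the plan says.** Three statements in the Protocol fix how the outcome is obtained.

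- **Definition** (Operational definitions, Birthweight): "birthweight of newborn is the first weight of the newborn obtained after birth", with LBW set at below 2,500 g whatever the gestational age.
- **Method** (Measurement of Birth weight): "During data collection, birth weight will be confirmed by weighing the baby using the metric scale (in grams". No age limit or time window is attached.
- **Exception** (same section): "Documented evidence on the child health card or verbally from the mother will only be used if the baby is ill". Ill is not defined, and the card is not expressly ranked above the mother's word.

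Two other places bear on the reading. Sampling techniques says that the women are "followed until delivery to see the incidence of low birth weight". The Introduction states: "Low birth weight is not only a predictor of prenatal morbidity and mortality".

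The printed questionnaire has no field labelled birth weight, source of birth weight, or age at weighing. Its only weight item is an unlabelled one listed between MUAC and height.

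**The concern.** Birth weight is the only dependent variable. It feeds both the logistic regression, through the 2,500 g cut, and the t test on means. Two problems follow from the text.

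First, the definition and the method need not give the same number. If the study weighing is not done at birth, a well baby's later weight stands in for the first weight. The child health card, which may hold the first weight, is closed to well babies by the restriction to ill ones.

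Second, the source of the outcome depends on the newborn's health. Well babies are weighed; ill babies are classified from a card or from the mother's word. The Introduction itself ties LBW to morbidity, so small babies plausibly fall more often under the second source.

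At stake are the LBW incidence, which the cohort is meant to observe, and to a lesser degree the association with anemia. Without fields for source and age at weighing, the affected values could not be identified afterwards.

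**Working it through.** **Inputs from the Protocol** (Sample size determination): LBW in non-anemic women p0 = 0.146, odds ratio 3.17, power 80%, 95% confidence, 78 per group (156), raised to 180 for 15% non-response.

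**Reproducing the plan's figure.** p1 = 3.17 × 0.146 / (0.854 + 3.17 × 0.146) = 0.4628 / 1.3168 = 0.3515. The two-proportion formula gives 68.3 per group, so 69 without continuity correction, and 77.7, so 78, with it. This matches the table, and 156 × 1.15 = 179.4, so 180. Nothing below changes the sample size.

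**Assumptions.** The Protocol gives no weight change, illness rate or recall accuracy. All such values below are assumed, and ranges are shown.

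**(a) Late weighing.** Take birth weight as normal with SD 500 g. Then the mean is 2,500 + 1.054 × 500 = 3,027 g in non-anemic women and 2,500 + 0.381 × 500 = 2,691 g in anemic women. If the study weight is f times the first weight in both groups, observed LBW = Φ((2,500/f − mean)/500).

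| f | LBW, non-anemic | LBW, anemic | OR |
|---|---|---|---|
| 0.93 | 24.9% | 49.8% | 2.99 |
| 0.95 | 21.5% | 45.3% | 3.03 |
| 0.97 | 18.4% | 41.0% | 3.08 |
| 1.00 | 14.6% | 35.1% | 3.17 |
| 1.03 | 11.5% | 29.9% | 3.28 |
| 1.05 | 9.8% | 26.8% | 3.36 |

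A wider variant shifts well babies only, by −200 to +400 g, and gives ill babies a recall error with SD 200 g. LBW in non-anemic women then runs from 24.5% to 6.0%, the OR stays within 2.89 to 3.34, and the mean difference is 320 to 370 g against a true 336 g.

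**(b) Different source for ill babies.** Let a be the share ill among LBW babies and b the share ill among the others. Weighing of well babies is taken as error-free, and every ill baby is classified by recall with sensitivity se and specificity sp. Observed proportion = p × (1 − a(1 − se)) + (1 − p) × b(1 − sp).

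- Mild case (a = 0.30, b = 0.05, se = 0.70, sp = 0.95): 0.146 × 0.91 + 0.854 × 0.0025 = 0.135, and 0.3515 × 0.91 + 0.6485 × 0.0025 = 0.3215. OR = 3.04.
- Severe case (a = 0.50, b = 0.10, se = 0.60, sp = 0.90): 0.146 × 0.80 + 0.854 × 0.01 = 0.1253, and 0.3515 × 0.80 + 0.6485 × 0.01 = 0.2877. OR = 2.82.

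Power at 78 per group, without continuity correction, falls from 0.85 to 0.80 in the mild case and 0.71 in the severe case. If half of the ill babies have an accurate card, the OR is 2.99 to 3.10; if three quarters do, 3.08 to 3.14.

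**Scale.** With 78 per group, SE(log OR) = √(1/27.4 + 1/50.6 + 1/11.4 + 1/66.6) = 0.399, so the 95% interval around 3.17 is about 1.45 to 6.93. The severe case lies ln(3.17/2.82)/0.399 = 0.29 standard errors from 3.17.

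**The case against.** The best defense is that confirming a weight presupposes one already on record, that the definition is unambiguous, and that follow-up ends at delivery. Read together, these place the weighing at or near birth, where the error in well babies would be small. No postnatal visit is described, so weighing days or weeks later is something a reader might infer but the text does not state. This stands as a possible reading. It does not remove the conflict, because no time is fixed and the word *only* still closes the card to well babies.

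Three stronger readings are tempting and are not supported.

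- **That the error depends on birth weight itself.** The rule turns on illness. The link to LBW is an inference through the Introduction's statement on morbidity, and no illness rate is given.
- **That the error differs by anemia status.** Nothing shows that illness or recall differs between anemic and non-anemic mothers at a given birth weight.
- **That babies born outside the selected hospitals get a late weighing or none.** Eligibility asks for "Plan to deliver in the region", and one block of the form is headed "Obstetric and baby characteristics of mothers who gave birth at the selected public Hospitals". A form sub-heading does not establish how births elsewhere are handled, and inclusion also requires that the woman can be contacted.

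It is also fair that the card is named before the mother's word. Treating every ill baby as classified by recall is therefore a worst case.

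**Conclusion.** The point holds as a conflict within the Protocol on its only outcome. The definition is the first weight, the method is an untimed weighing, and the source changes with the baby's health. It is more than a detail left for later, because it is a stated field rule and a first weight not recorded at birth may not be recoverable.

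The size is uneven. With SD 500 g and a study weight 7% below to 5% above the first weight, LBW in non-anemic women reads about 10% to 25% against 14.6%. Over both mechanisms the OR moves from 3.17 to about 2.8 to 3.4, which is small beside its sampling error. A reader might infer serious bias in the anemia association; these figures do not show it. All of them rest on assumed rates. The rule should be corrected before data collection, but it does not by itself undermine the main comparison.

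**What to change.** Reconcile the definition and the measurement section with one rule for every live birth, ill or well:

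1. Use the first weight taken at delivery: a study weighing within a stated short window after birth, otherwise the weight documented at delivery on the card or register.
2. Use the mother's verbal report only as a last resort.
3. Add form fields for birth weight in grams, its source, and age at weighing.
4. Keep verbal-only weights in the main analysis and add a sensitivity analysis without them. Dropping them from the main analysis would make outcomes missing mainly among ill babies, who are plausibly more often LBW, and so lower the estimated incidence.

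The cost is two or three extra form fields and some retrieval of delivery records. The sample size is unchanged.
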